| PHA | Phytohemagglutinin |
| PHI | Protected Health Information |
| PI | Principal Investigator |
| POMS-A | Profile of Mood States – Adolescent |
| REPA | Report of External Professional Activities |

CONFIDENTIAL

| | |
|-------|--|
| SAE | Serious Adverse Event |
| SHAPS | Snaith-Hamilton Pleasure Scale |
| TRD | Treatment-Resistant Depression |
| TEPS | Temporal Experience of Pleasure Scale |
| UTox | Urine Toxicology Screen |
| VA | Veterans' Affairs |
| WASI | Weschler Abbreviated Scale of Intelligence |

Study Summary

| | |
|---------------------------------------|--|
| Title | Open-label intravenous subanesthetic ketamine for adolescents with treatment-resistant depression |
| Protocol Number | CTSI 22225 |
| Phase | 2 |
| Methodology | Single group open-label pilot study |
| Study Duration | 2 years |
| Study Center(s) | University of Minnesota |
| Objectives | To determine the efficacy of repeated-dose subanesthetic IV ketamine among adolescent patients with treatment resistant depression. |
| Number of Subjects | 20 |
| Diagnosis and Main Inclusion Criteria | Male and female adolescents aged 12 to 18 with the presence of recurrent major depressive disorder without psychotic features. |
| Study Product, Dose, Route, Regimen | IV infusions of 0.5mg/kg of Ketamine hydrochloride over a 40-minute infusion period. Participants will receive a total of 6 doses over a 2-week period. |
| Duration of administration | 2 weeks |
| Reference therapy | Not applicable. |
| Statistical Methodology | 
The maximum effect of the ketamine infusions on symptoms for each participant will be assessed by conducting paired t tests between the lowest score from the post-treatment assessments and the baseline symptoms levels.
 
The time to relapse for each participant will be calculated and an average relapse time for the group will be reported.
 
Exploratory analysis will be done on changes in brain function, connectivity and chemistry, as well as in peripheral blood biomarkers.
 |

1 Introduction

This document is a protocol for a human research study. This study will be conducted according to US and international standards of Good Clinical Practice (FDA Title 21 part 312 and International Conference on Harmonisation guidelines), applicable government regulations and Institutional research policies and procedures.

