3.2 Primary Study Endpoints

The primary outcome measure is response status as defined by Children's Depression Rating Scale (CDRS) (Poznanski, 1985) Responders will be defined as having a significant reduction in their CDRS score ($\geq 50\%$) whereas non-responders will be defined as subjects whose scores do not show such a significant reduction or whose score increase. The percent change will be calculated by the formula below (Tao, 2009):

$$(\text{Baseline CDRS} - \text{Exit CDRS}) / (\text{Baseline CDRS} - 17)$$

Baseline CDRS: CDRS score obtained on Visit 1 – Baseline Assessment (Section 6.1)
Exit CDRS: the latest CDRS score obtained on Visit 10 - Clinical Assessment (Section 6.6) or Visit 11-16 – Follow-up Period (Section 6.7)

CONFIDENTIAL

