3.3 Secondary Study Endpoints

1. Montgomery-Åsberg Depression Rating Scale (MADRS) (Montgomery & Asberg, 1979) score of $\geq 50\%$. The MADRS has been used in most previous ketamine studies in adults and is designed to be sensitive to change. Although it has not been validated in adolescents, it has been used in several previous treatment studies of adolescent depression (Berard et al., 2006; von Knorring et al., 2006).
2. The Clinician-Administered Dissociative States Scale (CADSS) (Bremner et al., 1998)
3. The Profile of Mood States-Adolescent Version (POMS-A) (Terry et al., 1999)
4. The Beck Depression Inventory-II (Beck, 1988) which has been validated for adolescents (Osman et al., 2004)
5. The four-item positive symptom subscale of the Brief Psychiatric Rating Scale (BPRS) (Overall, 1962) consisting of suspiciousness, hallucinations, unusual thought content, and conceptual disorganization.
6. Relapse will be defined as a CDRS score $\geq 50\%$ of the pre-ketamine baseline. The onset of relapse will be calculated as the day halfway between the date of relapse and the previous date of response.
7. Biological endpoints will include MRI-based measures and blood-based measures of neuroplasticity.
8. The Clinical Global Impressions Scale (CGI) (Guy, 1976)

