4.1 Inclusion Criteria

Patients will be eligible to participate in the study if all of the following conditions exist:

- 1) Willing and able to provide informed consent and assent.
- 2) Male and female adolescents aged 12 to 18 years.
- 3) Presence of recurrent MDD confirmed by the K-SADS-PL (Kaufman et al., 1997).
- 4) Current depression severity measured by the Children's Depression Rating Scale (CDRS) (Poznanski, 1985) raw score greater than or equal to 36 at screening and the day ketamine is due to be received for the first time.
- 5) Current depressive episode resistant to treatment, defined as failure to achieve remission (elimination of symptoms and restoration of pre-morbid psychosocial functioning) from at least 2 antidepressant trials. Systematic evaluation of previous antidepressant trials will be assessed by using the Antidepressant Treatment History Form (Sackeim, 2001).
- 6) If present, current antidepressant medication treatment must be dose stable for at least 2 months prior to beginning the study*
- 7) Participants should have a medical history and physical examination in the 30 days prior to initiating the ketamine infusions.

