7.2 Subject Population(s) for Analysis

Data from each participant who completes the six ketamine treatments will be subjected to the primary study analysis. We will conduct secondary analyses on all participants who received at least one dose of treatment.

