7.3 Statistical Methods

In the following analyses, primary outcome measures will include the “per protocol” population. The secondary measures will include the “intent to treat” population.

Primary analysis: Paired t tests will be conducted between the lowest score from the post-treatment assessments and the baseline symptom levels to assess the maximum effect of ketamine infusion on symptoms for each person.

Secondary Analyses:

1. We will calculate the time to relapse for each participant.
2. Biological Mechanisms:
 - a. Neuroimaging data: Paired t tests will be conducted to evaluate pre- and post ketamine treatment changes in measures of brain functional activation, connectivity, white matter microstructure and brain metabolite concentrations. These preliminary data will be used to identify responsive measures and estimate sample sizes that would be needed to use these measures as endpoints in future studies.
 - b. Bimolecular studies to examine mechanisms of cellular resilience (insulin challenge, cytokine testing, gene expression) will be conducted to evaluate change in these pathways before and after ketamine. Analyses will be conducted by [name] at Mayo Clinic. Peripheral blood mononuclear cells (PBMCs) will be isolated from whole blood and divided into two groups. The first group will not receive any treatment. RNA will be extracted and whole genome microarray will be performed using illumina's genome-wide gene expression arrays. Differential pre- versus post-ketamine mRNA levels will be quantified and bioinformatics pathway analysis will be used to identify key differences in molecular responses to ketamine. A second subset of PBMCs will be cultured and cryopreserved. Once all samples are collected cells will be immortalized to ensure sufficient tissue availability. The following two separate analyses will then be performed:

CONFIDENTIAL

- i. Group 1 PBMCs will be stimulated with insulin and intracellular Akt, mTOR, and GSK3 gene and protein levels will be quantified following 0, 5, 15, and 30 minutes of stimulation. This signaling pathway is implicated in mediating the antidepressant response to ketamine. Western blot and rtPCR techniques will be used to quantify protein and gene expression, respectively;

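### The planned average relapse time has no rule for participants who have not relapsed, leave early or never respond, so what it measures is undefined

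*Combined protocol and SAP*

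**What the plan says.** The group summary appears only in the Study Summary, under Statistical Methodology: "The time to relapse for each participant will be calculated and an average relapse time for the group will be reported". Section 7.3 (Secondary Analyses, item 1) is shorter: "We will calculate the time to relapse for each participant". Section 7.2 fixes who is included: "We will conduct secondary analyses on all participants who received at least one dose of treatment".

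Section 3.3, item 6, defines relapse as a CDRS score of at least 50% "of the pre-ketamine baseline" and dates it as follows: "The onset of relapse will be calculated as the day halfway between the date of relapse and the previous date of response".

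Other sections bear on the point:
- Section 2 lists durability first among the secondary objectives, with a six-week window.
- Section 6.7 asks everyone, responder or not, to attend six weekly visits that include the CDRS.
- Section 4.4 foresees exits through withdrawal, non-response or relapse.
- Section 3.1 gives both a four-week observation period and six weeks of weekly assessments.
- Section 1.4 reports that half of the investigators' adult series had not relapsed at four weeks.

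No section gives a time origin, a censoring rule, a time-to-event estimator, or a way to score participants who have no relapse date.

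**The concern.** A relapse time is promised for every participant, but the dating rule needs two events: a response, then an observed relapse. Three groups have no such time: those still well at the last CDRS, those who leave before relapsing, and those who never respond. The adult series and Section 4.4 give reason to expect all three. A plain average cannot be formed until someone decides what to do with them, and different decisions give different quantities under the same name.

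The average is the only group summary of relapse time in the plan, and it serves the durability objective. If the rule is left open, it will be chosen after the data are seen, in an open-label study. One natural choice, averaging over relapsers only, would tell a reader little about durability if responses last about four weeks or longer.

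**Working it through.** The plan gives no expected relapse time or power figure, so there is nothing of its own to reproduce. The scenarios below are assumptions, not predictions, and they presume a relapse rule that does not overlap response. The 4-week median is taken from the adult series in Section 1.4; 8 weeks is its double; 2 weeks is the low end of the 2-3 weeks that Section 1.4 gives for other studies. Follow-up is six weeks.

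**1. Formulas.** Under a constant hazard, S(t) = exp(-λt) with λ = ln 2 / median.
- Relapse-free share at week 6: P = S(6).
- Mean with non-relapsers scored at week 6 (the restricted mean): R = (1 - P)/λ.
- Mean among relapsers only: (R - 6P)/(1 - P).

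**2. Effect of the missing rule, median 4 weeks.** λ = 0.1733 and P = exp(-1.040) = 0.354.
- Non-relapsers scored at week 6: R = 0.646/0.1733 = 3.73 weeks.
- Non-relapsers dropped: (3.73 - 6 × 0.354)/0.646 = 2.49 weeks.
- Scored at week 6, with 10% never-responders scored 0: 3.73 × 0.9 = 3.36 weeks. If never-responders are excluded, it stays 3.73.
- Early leavers scored at their last visit: (1 - exp(-6(λ+μ)))/(λ+μ), with μ = -ln(1 - d)/6 and d the share who would drop out by week 6. This gives 3.57 for d = 10% and 3.41 for d = 20%.

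**3. Does a relapser-only mean register durability?** At median 8 weeks, λ = 0.0866, P = 0.595 and R = 4.68, and the relapser-only mean is (4.68 - 3.57)/0.405 = 2.74. Doubling the median from 4 to 8 weeks therefore moves:
- the relapser-only mean from 2.49 to 2.74 weeks;
- the restricted mean from 3.73 to 4.68 weeks;
- the relapse-free share from 35% to 59%.

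With 18 responders (90% of 20, the adult response rate in Section 1.4), the simulated sampling SD of the relapser-only mean is about 0.5 to 0.7 week, larger than the 0.25-week shift.

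With Weibull relapse times, doubling the median gives:

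| Weibull shape | Relapser-only mean, median 2 to 4 (weeks) | Relapser-only mean, median 4 to 8 (weeks) | Relapse-free share, median 4 to 8 (points) |
|---|---|---|---|
| 0.7 | 0.26 | 0.17 | 17 |
| 1.0 | 0.46 | 0.25 | 24 |
| 1.5 | 0.86 | 0.37 | 36 |
| 2.0 | 1.26 | 0.47 | 47 |

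The relapser-only mean is thus flat from a median of about 4 weeks upward, and less so below that. At shape 2 it goes from 2.12 to 3.38 weeks as the median goes from 2 to 4.

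**4. Losses of response before Visit 10.** After the entry check, no CDRS is listed until Visit 10, up to 7 days after the last infusion (Sections 6.3, 6.4 and 6.6), so a response lost before then cannot be dated. With Visit 10 on day 7 and median 4 weeks:
- timed from the last infusion, the relapser-only and restricted means are 3.14 and 4.34, longer than 2.49 and 3.73;
- timed from Visit 10 with five weeks left, they are 2.14 and 3.34, shorter;
- if six full weeks follow Visit 10, a constant hazard gives 2.49 and 3.73 again.

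The direction depends on the unstated origin.

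**5. Response against relapse.** Section 3.2 defines response as (B - X)/(B - 17) of at least 0.5, so X is at most (B + 17)/2. Section 3.3, read as a raw score, defines relapse as X of at least B/2. With one baseline the overlap is (B + 17)/2 - B/2 = 8.5 points. At B = 60, response is X up to 38.5 and relapse is X from 30; at B = 36, they are 26.5 and 18. If relapse is also meant to subtract 17, the overlap disappears except at an exact tie.

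The baseline is not clearly common to both rules. Section 3.2 says "Baseline CDRS: CDRS score obtained on Visit 1", Section 3.3 speaks of the score before ketamine, and Section 4.1 requires a qualifying CDRS "at screening and the day ketamine is due to be received for the first time".

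**The case against.** The strongest reply is that the harm is conditional. The plan does not say that non-relapsers will be dropped. Scoring them at week 6, with nobody leaving early, gives a valid six-week restricted mean that needs only the right label. The average appears only in the Study Summary; Section 7.3 plans individual times, which could simply be listed for 20 participants. Section 3.3 supplies midpoint dating, and Sections 2 and 3.1 hint at an origin at the last infusion. Weekly CDRS is requested from everyone, so a sound analysis could still be done later. The proposed estimate will be imprecise.

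All of this stands, and it limits the weight of the point. It does not remove the gap: a listing also has no entry for participants without a relapse date, and a restricted mean is one of several conventions among which the plan does not choose.

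A reader might also infer that a relapser-only average is insensitive at any duration. It is not: at medians of 2 to 4 weeks, a range that Section 1.4 makes plausible, it moves by 0.26 to 1.26 weeks.

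**Conclusion.** The plan promises a relapse time for each participant that its own definition cannot supply, and a group average whose meaning rests on an unstated rule. In the base scenario that rule alone moves the average between 2.5 and 3.7 weeks. If non-relapsers are dropped, the average is a poor measure of durability when the median is about 4 weeks or longer. These sizes rest on the assumed Weibull or constant hazards and on six weeks of follow-up.

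Three stronger readings are not supported:
- That undatable early losses lengthen the average. This holds only if time runs from the last infusion.
- That the result would err in a known direction against adults. The documents do not say how the adult durations were summarised.
- That a participant relapsed at week 6 must count as a primary non-responder, because Section 3.2 takes as Exit "the latest CDRS score obtained on Visit 10" or at a later follow-up visit. Under the raw-score reading, a week-6 score of 30 to 38 at baseline 60 is both relapse and response.

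This is an exploratory secondary outcome in a 20-person pilot with no planned test. It should be changed, but the priority is modest.

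**What to change.** Two matters come first:
1. Reconcile the response rule in Section 3.2 with the relapse rule in Section 3.3, state which baseline CDRS each uses, and define response at the visit level so that a previous date of response exists.
2. Reconcile the four-week and six-week statements in Section 3.1, which set the censoring time.

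Then revise the Study Summary and Section 7.3:
3. Replace the average with a Kaplan-Meier or interval-censored estimate of time to relapse among participants in response at Visit 10. Start the clock at Visit 10, or at the last infusion with delayed entry at Visit 10, and censor at the last weekly CDRS.
4. Label it as durability given response at Visit 10. It does not recover earlier losses and leaves out those who first respond at Visits 11-16. Report separately the numbers of later first responders, never-responders and censored participants.
5. Give relapse-free proportions with 95% confidence intervals at weeks that everyone can reach (only 5 to 6 weeks after Visit 10 if follow-up ends six weeks after the last infusion). Give the median only if it is reached; add a restricted mean to the same horizon if wanted.
6. For all treated, report the proportion in response at week 6. Count exits for non-response or relapse as not in response, and state a rule for other leavers.

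The cost is one endpoint-definition decision, some analysis wording and a standard method, with no new data. The downside is wide intervals (exact binomial): 8 of 18 gives 22% to 69%, and 8 of 20 gives 19% to 64%. With a true median of 8 weeks, a constant hazard and 18 in response at Visit 10, the median would be reached within five weeks of that visit in only about 14% of trials.

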1.1 Background

Depression frequently emerges during adolescence and is associated with severe outcomes. Current interventions do not lead to remission for many adolescents. Treatment-resistant depression (TRD) in adolescence is an ominous prognostic indicator for a lifetime of suffering and increased risk for suicide. Efforts should be directed toward novel interventions that could alter this perilous course. Theoretically, restoration of healthy development during this critical window would substantially improve outcomes over the lifespan.

Ketamine is a noncompetitive, high-affinity antagonist of the *N*-methyl-D-aspartate type glutamate receptor that has long been used for induction and maintenance of anesthesia in children and adults, and recently has been investigated for its rapid antidepressant effects.

No results from any studies examining effectiveness of either single-dose or serial-dose ketamine have yet been published in adolescents with TRD. Because of the ongoing neurodevelopment in adolescence, which is thought to confer enhanced neuroplasticity, it is possible that adolescents with TRD could show greater responses and more sustained remission than adults with TRD. The biological mechanisms of depression impacted by ketamine are only now being uncovered in adults (Zarate et al., 2013). Characterization of the neural mechanisms underlying ketamine response or non-response in adolescents with TRD will represent a significant advance.

1.2 Investigational Agent

The effects of ketamine are mediated by *N*-methyl-D-aspartate, opioid, muscarinic and different voltage-gated receptors. It has hypnotic, analgesic and amnesic effects (Sinner & Graf, 2008). Ketamine is water and lipid soluble, which allows it to be administered in different ways (intramuscularly, intravenously, intranasally, rectally and orally) and distributes widely throughout the body including crossing the blood brain barrier. It has a molecular weight of 274.4M, its chemical formula is C₁₃H₁₆ClNO, and its melting point is between 258°C and 261°C (Sinner & Graf, 2008). The IV dose used for anesthesia ranges between 1 to 4.5 mg/kg (Elia & Tramer, 2005; Sinner & Graf, 2008). The median dose for analgesia is 0.4 mg/kg (Elia & Tramer, 2005), similar to that used for depression. Dose reported in the drug abuse literature is typically 1/8 g usually taken intranasally. Metabolism of ketamine is primary hepatic and it is excreted in the urine; metabolism half-life is 2.5-3 hours (Sinner & Graf, 2008).

CONFIDENTIAL

This material is the property of the University of Minnesota. Do not disclose or use except as authorized in writing by the study sponsor

[figure not shown]
1.3 Preclinical Data

Despite the fact that depression frequently emerges during adolescence (Kessler & Walters, 1998) and that many adolescents do not respond to treatment (March et al., 2004), ketamine has not yet been tested in adolescents. However, recent research using animal models of depression has suggested that repeated doses of ketamine alleviated depressive behaviors in both adolescent and adult rats (Parise et al., 2013). Due to the enhanced neuroplasticity associated with the developing brain, adolescents with TRD may show greater and more sustained response to ketamine than adults with TRD.

1.4 Clinical Data to Date

Randomized, double-blind, saline-controlled trials in adults with TRD have demonstrated that a single, subanesthetic infusion of intravenous (IV) ketamine at 0.5 mg/kg over 40 minutes can produce a rapid (within 2 hours) antidepressant response (Ibrahim et al., 2011; Zarate et al., 2006). Recent evidence suggests that serial doses of ketamine may be even more effective and may lead to more prolonged remission (aan het Rot et al., 2010; Murrough et al., 2012). Our current research with using serial dosing of IV ketamine among adult veterans with TRD over a 2-week period has shown promising results, with a response rate of 92% among the 12 participants to date.

Our motivation to test the efficacy of IV ketamine in adolescents with TRD stems in part from our encouraging experience testing repeated-dose IV ketamine in adult veterans with TRD (PI [name]) at the Veterans' Affairs (VA) Medical Center in Minneapolis (Shiroma, *Journal of Affective Disorders* 2013, *in press*). Patients receive 6 infusions of IV ketamine 0.5mg.kg over 60 minutes, with infusion visits occurring 3 times weekly for 2 weeks with no "wash-out" period. So far, as indicated below, a 90% cumulative response rate has been observed. The duration of response (i.e. time to relapse) has been considerably longer than other studies (i.e. 2-3 weeks (Murrough et al., 2013)). At 4 weeks, 50% of the patients in our study have still not relapsed. Ten adults have completed treatment to date.

[figure not shown]
With its rapid onset of action, ketamine provides an ideal tool for the study of biomarkers in major depressive disorder (MDD). Prior studies have used neuroimaging, including functional magnetic resonance imaging (fMRI) (Scheidegger et al., 2012), positron emission tomography (PET) (Carlson et al., 2013), and magnetoencephalography (MEG) (Salvadore et al., 2009; Salvadore et al., 2010), and proton magnetic resonance spectroscopy (proton MRS) (Salvadore et al., 2012) in ketamine trials to further elucidate the underlying biological mechanisms of MDD. We have been developing tools for examining neural circuitry in adolescents with MDD (Cullen et al., 2009; Cullen et al., 2010) which we plan to apply in the proposed study to examine neural mechanisms of ketamine action.

Another avenue for understanding the mechanisms of response to ketamine in TRD is to examine the cellular mechanisms associated with stress and resilience. MDD and other mental illnesses provide significant stress on an individual, and research has shown that there are deleterious neurobiological effects that result from chronic stress. Allostatic overload occurs in certain chronic medical disorders that are associated with chronic stress such as mood disorders (Brietzke et al., 2011). Allostatic overload leads to compromised resilience, rendering the organism more vulnerable to disease (Karatsoreos & McEwen, 2011). Evidence suggests that there is a correlation between enhanced cellular aging, as seen by reduced telomerase activity and telomerase length, and TRD (Wolkowitz et al., 2012) and it is hypothesized that allostatic overload is the driving factor. Insulin signaling and cytokine responses are two key cellular pathways that are chronically altered through the process of allostatic overload over time (Tanti et al., 2013). We hypothesize that the rapid effects of ketamine to reverse depression symptoms may occur via reversal of these systems. Through experimental procedures including white blood cell challenge, we hope to identify how these key cellular adaptations are associated with disease severity and treatment response to ketamine.

